17.2.1. ALL TEAEs

Incidence of TEAEs will be presented by System Organ Class (SOC) and Preferred Term (PT) and also broken down further by maximum severity for each phase, each dose and disease cohort and overall. The study drug related TEAEs will also be summarized in the similar way.

17.2.1.1. Severity

AE severity will be graded to 5 grades (Grade 1 to Grade 5) according to the national cancer institute common terminology criteria for adverse event (NCI CTCAE) V4.03.

TEAEs starting after the first dose of study medication with a missing severity will be classified as Grade 3. If a patient reports a TEAE more than once within that SOC/ PT, the AE with the worst-case severity will be used in the corresponding severity summaries. A summary table for TEAE with grade ≥ 3 will also be presented by dose or disease cohort.

17.2.1.2. Relationship to Study Drug

The relationship, as indicated by investigator, is classed as “Unrelated” and “Related”. A study drug “related” TEAE is defined as a TEAE with response of “Yes” to the field “Possible causality to study drug?” on the “Adverse Event (AE)” form of the eCRF. TEAEs with a missing causality to study drug will be regarded as “Related” to study drug. If a patient reports the same AE more than once within that SOC/ PT, the AE with the worst case relationship to study drug will be used in the corresponding relationship summaries.

Document: [REDACTED]

Author: [REDACTED] Version Number: 2.5
Version Date: 18Feb2022

Template No.: [REDACTED] Reference: CS_WI_BS005

Effective Date: 02Dec2019

17.2.2. TEAEs LEADING TO DOSE INTERRUPTION OR REDUCTION

TEAEs leading to dose interruption or reduction will be identified as those TEAEs with a response of either “Drug Interrupted” or “Dose Reduced”.

For TEAEs leading to dose interruption or reduction, summaries of incidence rates (frequencies and percentages) by SOC and PT will be prepared. Summaries for TEAEs leading to dose interruption or reduction by SOC and PT will be further limited to study medication-related TEAE and broken down by maximum severity.

17.2.3. TEAEs LEADING TO DISCONTINUATION OF STUDY DRUG

TEAEs leading to permanent discontinuation of study drug will be identified as those TEAEs with a response of “Drug Withdrawal”.

For TEAEs leading to discontinuation of study drug, summaries of incidence rates (frequencies and percentages) by SOC and PT will be prepared. Summaries for TEAEs leading to discontinuation of study drug by SOC and PT will be further broken down by maximum severity and strongest relationship to study drug.

TEAEs leading to discontinuation of study drug will also be listed.

17.2.4. SERIOUS ADVERSE EVENTS

Serious adverse events (SAEs) are those events recorded with a response of “Yes” for the field “Is the adverse event serious?” on the “Adverse Events (AE)” form of eCRF. A summary of serious TEAEs by SOC and PT will be prepared. In addition, summaries for serious TEAEs by SOC and PT will be further broken down by maximum severity.

Listing of serious TEAE will also be provided.

17.2.5. ADVERSE EVENTS LEADING TO DEATH

TEAEs leading to Death are those events with response of “Fatal. A summary of TEAEs leading to death by SOC and PT will be prepared.

TEAEs leading to death will also be listed.

17.2.6. ADVERSE EVENTS OF SPECIAL INTEREST (AESI)

According to the IB Version 13.0 (dated 08 November 2021), treatment emergent adverse events of special interest (TEAESI) for fruquintinib are defined to include 10 categories:

- hepatic function abnormal
- haemorrhages
- hypertension
- infections
- thyroid dysfunction
- proteinuria
- dermatological toxicity
- gastrointestinal perforation

Document: [REDACTED]

Author: [REDACTED]

Version Number:

2.5

Version Date:

18Feb2022

Template No.: [REDACTED]

Reference: CS_WI_BS005

Effective Date: 02Dec2019

- embolic and thrombotic events
- left ventricular ejection fraction decreased

The MedDRA terms used to define AESIs categories are listed in Table 2, for AESI categories (i.e. “haemorrhages”, “hepatic function abnormal”, “hypertension”, “proteinuria”, “thyroid dysfunction”, “embolic and thrombotic events” “gastrointestinal perforation” and “left ventricular ejection fraction decreased”), the PTs to be included in these AESI categories are included in [Appendix 5](#). These terms were selected by subjecting standardized MedDRA queries (SMQ) lists (narrow and/or broad scope depending on the category) for each category and had been used in the fruquintinib clinical development program for pharmacovigilance. TEAESI will be summarized by AESI category and PTs. Incidence rates (frequencies and percentages) will be presented by treatment arm. Similar by severity and by relationship summary tables will also be provided separately.

Table 2: MedDRA Terms Used for Adverse Events of Special Interest

AESIs Category	Search terms/strategy
Dermatological toxicity	MedDRA SOC “skin and subcutaneous tissue disorders”
Hypertension	MedDRA SMQ “hypertension” (narrow)
Thyroid dysfunction	MedDRA SMQ “thyroid dysfunction” (broad)
Proteinuria	MedDRA SMQ “proteinuria” (narrow)
Hepatic function abnormal	MedDRA SMQ “drug related hepatic disorders-comprehensive search” (narrow)
Haemorrhages	MedDRA SMQ “haemorrhages” (narrow)
Infections	MedDRA SOC “infections and infestations”
Embolic and thrombotic events	MedDRA SMQ “embolic and thrombotic events” (narrow)
Gastrointestinal perforation	MedDRA SMQ “gastrointestinal perforation” (narrow)
Left ventricular ejection fraction decreased	MedDRA SMQ “cardiac failure” (narrow)

Time to first TEAESI will also be summarized by AESI category for each dose and/ or disease cohort in each study phase. Time to first TEAESI is defined as time interval from date of first administration of study treatment to the earliest onset date among TEAEs within the same AESI categories. That is, if a patient has multiple AEs occurrences under the same AESI category, the earliest AE onset date will be used as the first onset date to the AESI category.

17.3. DEATHS

Data on death will be listed, along with results of total number of patients died and cause of death summarized. Result of patients with on-study death, which is defined as the death after the first dose until 37 days after last dose, will also be tabulated. On-treatment death will be flagged.

17.4. LABORATORY EVALUATIONS

Results from the local laboratory will be included in the reporting of this study for Hematology, Serum chemistry, Coagulation, Urinalysis, 24-hours urine protein, and Thyroid function test.

Document: [REDACTED]

Author: [REDACTED]

Version Number:

2.5

Version Date:

18Feb2022

Template No.: [REDACTED]

Reference: CS_WI_BS005

Effective Date: 02Dec2019

Indexes collected for laboratory assessments are shown in table below:

Laboratory Test	Parameters
Hematology	red blood cell [RBC] count, hemoglobin, platelet count, white blood cell [WBC], neutrophils, lymphocytes, monocytes, eosinophils, basophils, hematocrit, reticulocyte count
Coagulation	activated partial thromboplastin time [aPTT], international normalized ratio [INR]
Serum chemistry	total protein, albumin, glucose, blood urea nitrogen [BUN], creatinine, creatinine clearance, alkaline phosphatase [ALP], lactate dehydrogenase [LDH], total bilirubin, Aspartate Aminotransferase [AST], Alanine Aminotransferase [ALT], calcium, magnesium, potassium, sodium, chloride, total cholesterol, triglycerides, uric acid, bicarbonate, phosphorus
Urinalysis	pH, glucose, protein, and blood
Thyroid function	thyroid stimulating hormone [TSH], free T3, and free T4

The non-protocol specified tests and urinalysis results will not be summarized; they will only be included in listings. Data recorded by the laboratory will be converted to the International System of Units (SI) and all presentations will use SI units. Quantitative laboratory measurements reported as “< X”, i.e., below the lower limit of quantification (LLQ), or “> X”, i.e., above the upper limit of quantification (ULQ), will be converted to X for the purpose of quantitative summaries, but will be presented as recorded, i.e., as “< X” or “> X” in the listings. Quantitative data collected between after date of ICF and up to 37 days following the last dose of study medication will be used for analysis. The following summaries will be provided for laboratory data:

- Observed value and change from baseline by visit (for quantitative measurements)
- Shift from baseline to worst post-baseline CTCAE toxicity for laboratory abnormalities
- Shift from baseline to the worst post-baseline investigators’ assessment (i.e., normal, abnormal but not clinically significant [NCS], abnormal and clinically significant [CS] for quantitative measurements and categorical measurements)

Both the scheduled and unscheduled assessments will be used to identify the worst post-baseline values.

Listing of all laboratory data by patients, abnormal values identified according to normal range (low, normal and high) by programming and markedly abnormal criteria by investigators’ assessment will be flagged.

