
Safety Assessment
	
All patients who have received at least one dose of fruquintinib will be included in the safety analysis set (SAS).
 
All DLTs will be listed by dose cohort in DLT-evaluable patients for the dose escalation phase only.
 
Safety will be evaluated based on the frequency and severity of AEs, change of laboratory test results, changes in vital signs, change in ECG, and change in echocardiogram. Safety data will be listed and summarized by dose cohort, for patients overall, and for patients with mCRC (cohorts' B and C) and mBC (cohorts' D and E) who received fruquintinib at the RP2D.
 
The severity of all AEs will be graded by the investigator according to the NCI CTCAE v4.03. All AEs will be coded using the Medical Dictionary for Drug Regulatory Activities (MedDRA). Treatment-emergent AEs (TEAEs) will be classified by MedDRA System Organ Class (SOC) and specified by Preferred Term (PT). The incidence of TEAEs, SAEs, adverse events of special interest (AESIs), TEAEs leading to dose interruption, dose reduction, or study drug discontinuation will be summarized.
 
For the laboratory assessments, such as hematology, serum biochemistry, urinalysis, and other urine parameters will be programmatically graded according to CTCAE severity grade. Summary tables will be presented to show the number of patients by CTCAE severity grade with

	
corresponding percentages. For parameters for which a CTCAE scale does not exist, the frequency of patients with values below, within, and above the normal ranges will be summarized. Shift tables for selected hematology and serum biochemistry will also be presented showing change in CTCAE severity grade from baseline to worst grade post-baseline.

Pharmacokinetics	
All patients who received at least one dose of fruquintinib and have at least one plasma sample obtained and analyzed will be included in the Pharmacokinetic Analysis Set (PKAS).
 
A non-compartmental model analysis will be performed for plasma concentration data by the central laboratory using WinNonlin (enterprise version). The following summary statistics will be presented for concentration data and PK parameters, where appropriate: mean, standard deviation, coefficient of variation (CV%), median, minimum, maximum, geometric mean, and geometric mean CV%.

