**Table 10 Dose Modification for Proteinuriaa**

AE Grading Standard	Dose Adjustment	Treatment Suggestions
Grade 1: Proteinuria 1+ by urinalysis;  24-hour urine protein quantitation <1.0 g	None	Follow up at scheduled study visits.
Grade 2: Proteinuria 2+ by the urinalysis;  24-hour urine protein quantitation is between 1.0 to <2.0 g	None	Provide supportive treatment and increase the frequency of urine monitor to once a week; consult nephrologist if necessary.
Grade 2: Proteinuria 2+ or above by urinalysis;  24-hour urine protein quantitation is between 2.0 to <3.5 g (excluding 3.5 g)	The drug can be interrupted and then reduced to lower if the AE recovers to Grade 1 or baseline level within 14 days.	Provide supportive treatment and increase the frequency of urine monitor to once a week; consult nephrologist if necessary.
Grade 3: 24-hour urine protein quantitation ≥3.5 g	The drug can be interrupted and then reduced to lower dose level if AE recovers to Grade 1 or baseline level within 14 days.	Provide supportive treatment and increase the frequency of urine monitor to once or twice a week; consult nephrologist if necessary. Should the same AE occur for 3 times or still occurs after 2 times of dose reduction, the drug should be terminated.

a: If protein ≥ 2+ on urinalysis during the study, a 24-hour urine test should be conducted within 1 week, and dose modification will be done by the result of 24-hour urine protein quantitation.

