### 8.3 Safety Analysis

Safety will be assessed through AEs, laboratory assessments, vital signs, and ECG results. Safety data will be listed and summarized by dose cohort across the 2 phases. All DLT events will be listed by dose cohort for the dose escalation phase only.

Severity of AEs will be graded by the investigator according to NCI CTCAE v4.03. If a CTCAE criterion does not exist, the grade corresponding to the appropriate adjective will be used by the investigator to describe the maximum intensity of the adverse event: Grade 1 (mild), Grade 2 (moderate), Grade 3 (severe), Grade 4 (life threatening), or Grade 5 (fatal) (see Section 7.1.6). All AEs will be coded with Medical Dictionary for Drug Regulatory Activities (MedDRA).

All AEs will be listed. The focus of safety data summarization will be on treatment-emergent adverse events (TEAEs), which are defined as AEs that occur or worsen in the period extending from the first dose of study drug to 30 days after the last dose of study drug in this study.

TEAEs will be summarized as the number of patients and corresponding percentage by MedDRA System Organ Class (SOC) as well as Preferred Term (PT). The incidence of TEAEs, SAEs, adverse events of special interest (AESIs), AEs leading to dose interruption, reduction, or treatment discontinuation will be presented by SOC and PT; by relationship to the investigational product and by toxicity grade for each dose level. Changes in laboratory data will be summarized by severity grade using the NCI CTCAE v4.03. When abnormal laboratory results at the patient level are counted, the worst value during study treatment will be chosen.

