Template No.: [REDACTED]

Reference: CS_WI_BS005

Effective Date: 02Dec2019

Aspartate Aminotransferase (IU/L)		Aspartate aminotransferase increased	>ULN - 3.0 x ULN	>3.0 - 5.0 x ULN	>5.0 - 20.0 x ULN	>20.0 x ULN
Alanine Aminotransferase (IU/L)		Alanine aminotransferase increased	>ULN - 3.0 x ULN	>3.0 - 5.0 x ULN	>5.0 - 20.0 x ULN	>20.0 x ULN
Serum Calcium (mmol/L)		Hypercalcemia	>ULN - 2.9 mmol/L	>2.9 - 3.1 mmol/L	>3.1 - 3.4 mmol/L	>3.4 mmol/L
	Hypocalcemia		<LLN - 2.0 mmol/L	<2.0 - 1.75 mmol/L	<1.75 - 1.5 mmol/L	<1.5 mmol/L
Magnesium (mmol/L)		Hypermagnesemia	>ULN - 3.0 mg/dL; >ULN - 1.23 mmol/L	~	>3.0 - 8.0 mg/dL; >1.23 - 3.30 mmol/L	>8.0 mg/dL; >3.30 mmol/L
	Hypomagnesemia		<LLN - 1.2 mg/dL; <LLN - 0.5 mmol/L	<1.2 - 0.9 mg/dL; <0.5 - 0.4 mmol/L	<0.9 - 0.7 mg/dL; <0.4 - 0.3 mmol/L	<0.7 mg/dL; <0.3 mmol/L
Potassium (mmol/L)		Hyperkalemia	>ULN - 5.5 mmol/L	>5.5 - 6.0 mmol/L	>6.0 - 7.0 mmol/L	>7.0 mmol/L
	Hypokalemia		<LLN - 3.0 mmol/L	~	<3.0 - 2.5 mmol/L	<2.5 mmol/L
Sodium (mmol/L)		Hypernatremia	>ULN - 150 mmol/L	>150 - 155 mmol/L	>155 - 160 mmol/L	>160 mmol/L
	Hyponatremia		<LLN - 130 mmol/L	-	<130 - 120 mmol/L	<120 mmol/L
Total cholesterol (mmol/L)		Cholesterol high	>ULN - 300 mg/dL; >ULN - 7.75 mmol/L	>300 - 400 mg/dL; >7.75 - 10.34 mmol/L	>400 - 500 mg/dL; >10.34 - 12.92 mmol/L	>500 mg/dL; >12.92 mmol/L

Document:

Author:

Template No.:

Effective Date: 02Dec2019

Version Number:

Version Date:

Reference: CS_WI_BS005

2.5

18Feb2022

Bilirubin (umol/L)		Blood bilirubin increased	>ULN - 1.5 x ULN	>1.5 - 3.0 x ULN	>3.0 - 10.0 x ULN	>10.0 x ULN
Triglycerides (mmol/L)		Hypertriglyceridemia	150 mg/dL - 300 mg/dL; 1.71 mmol/L - 3.42 mmol/L	>300 mg/dL - 500 mg/dL; >3.42 mmol/L - 5.7 mmol/L	>500 mg/dL - 1000 mg/dL; >5.7 mmol/L - 11.4 mmol/L	>1000 mg/dL; >11.4 mmol/L
Urinary protein		Proteinuria	1+ proteinuria; urinary protein <1.0 g/24 hrs	2+ proteinuria; urinary protein 1.0 - 3.4g/24hrs	urinary protein >= 3.5g/24hrs	~

Document: [REDACTED]

Author: [REDACTED]

Template No.: [REDACTED]

Effective Date: 02Dec2019

Version Number: 2.5

Version Date: 18Feb2022

Reference: CS_WI_BS005

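### SAP 17.4 makes urinalysis listings-only, against the protocol synopsis and the SAP's own proteinuria grading, and the protocol's range-frequency table is also absent; SAP 2.4 declares neither change

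*SAP*

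**What the plan says.** **Protocol.** The synopsis (Safety Assessment) says that laboratory assessments "such as hematology, serum biochemistry, urinalysis, and other urine parameters will be programmatically graded according to CTCAE severity grade". It continues: "Summary tables will be presented to show the number of patients by CTCAE severity grade with" percentages. For parameters that have no CTCAE scale, "the frequency of patients with values below, within, and above the normal ranges will be summarized". Section 8.3 repeats the general rule, with no exception for urine: "Changes in laboratory data will be summarized by severity grade using the NCI CTCAE v4.03".

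**SAP.** Section 17.4 names urinalysis and 24-hour urine protein as separate laboratory categories and lists the urinalysis panel as pH, glucose, protein and blood. It then says: "The non-protocol specified tests and urinalysis results will not be summarized; they will only be included in listings". The planned summaries that follow are:
- observed values and changes by visit;
- a shift table to the worst CTCAE grade;
- a shift table of the investigator's assessment.

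Section 17.4.2 grades laboratory results by Appendix 6 and tabulates treatment-emergent abnormalities by CTCAE term, grade and visit. The proteinuria row of Appendix 6 defines Grade 2 as "2+ proteinuria; urinary protein 1.0 - 3.4g/24hrs" and Grade 1 as 1+ or less than 1.0 g in 24 hours. Section 17.4.3 classifies values as low, normal or high.

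**The concern.** A programmer cannot follow both the listings-only sentence and the proteinuria grading. The choice decides whether the tables show the lowest grade of one of the drug's most frequent identified risks. Protocol Table 3 gives proteinuria at 52.1%, and SAP 17.2.6 makes it an adverse event of special interest.

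The adverse event tables do not fully replace the measured values. The special-interest summary is built from MedDRA terms, and protocol 7.1.8.4 says that not every laboratory abnormality qualifies as an adverse event. An asymptomatic 1+ dipstick that needs no action may never be recorded as one.

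The range-frequency table raises a smaller point of the same kind: the protocol promises a summary that the SAP does not plan.

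**Working it through.** No sample size, power or event count is involved, so this is a reconciliation of text.

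1. **Protocol against SAP on urinalysis.** The synopsis names urinalysis among the assessments to be graded and tabulated. SAP 17.4 removes it from all summaries.

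2. **Is the change declared?** SAP 2.4 lists five changes: the definition of the efficacy set, which endpoints use that set, subsequent therapy, Hy's Law and DILI. Urinalysis is not among them, and neither is the range-frequency table.

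3. **SAP against itself.** Appendix 6 grades dipstick 1+ and 2+. Section 17.4.2 tabulates every CTCAE-defined treatment-emergent abnormality without excepting urine, and the CTCAE shift table in 17.4 has no exception either. Appendix 4 assigns visit windows to urinalysis, although section 5.4 uses windows for visit-based summaries. All of these imply tabulation.

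4. **What is lost if the 17.4 sentence is followed?**
   - The 24-hour protein is a separate category that the sentence does not name, so it stays in the tables.
   - On treatment, the 24-hour test follows a dipstick of 2+ or more, within 1 week (protocol Appendix A note 10; Table 10 footnote). A 1+ finding triggers none, so it has no protocol-required 24-hour value and appears only in a listing.
   - At screening, a 24-hour collection is required only above 1+, and a dipstick of 2+ or more is itself exclusionary (exclusion criterion 7). Most enrolled patients would therefore have no protocol-required baseline 24-hour value. The dipstick is the scheduled urine protein measure and the only workable baseline for a shift table.

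5. **Completeness of the Appendix 6 row.** Its dipstick criterion stops at 2+. A higher dipstick reading with no 24-hour result has no stated laboratory grade.

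6. **Range frequencies.** TSH, free T3 and free T4 have no row in Appendix 6. Section 17.4.3 derives low, normal and high, but the only use stated in 17.4 is to flag listings. No table of patients below, within and above range is planned.

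**The case against.** Several parts of the opposing case stand.

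- **The sentence is ambiguous.** The words about non-protocol tests could also qualify urinalysis, which would leave the protocol panel summarized. This is possible but weak: non-protocol urine tests are already covered by the first part of the phrase, so the second part would add nothing.
- **The table shells are not visible.** SAP 7 places table content in mock shells. They may settle the matter, but the SAP text does not.
- **The protocol promises less than a urine shift table.** Its synopsis limits shift tables to selected hematology and biochemistry. For urine it promises tables by grade. The CTCAE shift table is the SAP's own commitment in 17.4.
- **The range omission may be deliberate.** The SAP modification history records the removal of a low/high/normal shift table at version 0.2. A shift table is not a frequency table, however, and the current synopsis still promises the latter.

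Four stronger inferences are tempting, and the documents do not support them.

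- A reader might infer that proteinuria would rest on investigator reporting alone. It would not: 24-hour protein is not excluded, and every on-treatment dipstick of 2+ or more should produce one.
- A reader might compute 0.521 × 128 = 66.7 and speak of about 67 patients with no measured-value table. That counts the wrong group. Table 3 gives an overall frequency for proteinuria, not the frequency of 1+ findings without a 24-hour value.
- A reader might infer that thyroid results are left to the investigator's judgement. SAP 17.4 gives quantitative tests observed-value and change-from-baseline tables, and Appendix 4 sets thyroid visit windows.
- A reader might complete Appendix 6 from protocol Table 10, where one row reads "Proteinuria 2+ or above by urinalysis". That row concerns dose modification and is tied to a 24-hour value of 2.0 to below 3.5 g. It is not a laboratory grade.

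**Conclusion.** The contradiction is real and undeclared, and it should be corrected. As written, the SAP does not determine whether dipstick proteinuria is tabulated. If the listings-only sentence governs, the loss is confined to dipstick-only findings: mainly Grade 1, plus any reading of 2+ or more for which the 24-hour test was not done. Proteinuria adverse events and 24-hour results remain in the tables. No patient count can be attached, because the documents give no rate for 1+ findings.

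The range-frequency gap is separate and narrower: one promised table is missing, while the measured thyroid values are still summarized.

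This conclusion assumes the more natural reading of the 17.4 sentence and that the unseen shells do not already resolve it. The study tests no hypotheses, so the consequence is incomplete safety description and not a wrong inference.

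**What to change.** 1. In SAP 17.4, limit the listings-only rule to non-protocol tests and to urine pH, glucose and blood.
2. State that urine protein is graded by Appendix 6, with the 24-hour result taking precedence over the dipstick that triggered it where both exist, and that it enters the 17.4 CTCAE shift table and the 17.4.2 treatment-emergent tables.
3. In Appendix 6, state how a dipstick above 2+ with no 24-hour result is graded. This rule is for laboratory tabulation only and leaves protocol Table 10 untouched.
4. Add the protocol's frequency table of patients below, within and above range for tests without a CTCAE scale (for example TSH, free T3 and free T4), using the 17.4.3 categories.

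If the sponsor prefers listings only for urinalysis, or no range table, both departures should be declared in SAP 2.4 and the dipstick criteria removed from Appendix 6 so that the SAP agrees with itself.

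The cost is SAP wording, one added table, and urine protein rows in tables already planned. No new data are needed.
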